1.2.5.2. Immunogenicity Parameters

The primary immunogenicity endpoints are as follows:

- Geometric mean titers (GMT) of Marburg GP protein-specific IgG antibody as measured by ELISA on Days 1 and 29
- GMT of PsVNT₅₀ and PsVNT₈₀ MARV GP-specific neutralizing antibody titers (the reciprocals of the serum dilutions at which 50% and 80% of the input pseudovirion was neutralized, respectively) as measured by Pseudovirion neutralization assay (PsVNA) on Days 1 and 29

If the corresponding titer value is below the lower limit of quantitation (LLOQ), the titer value will be considered as LLOQ/2 at such visit for GMT computation. For ELISA titers below limit of detection (LOD), the titer will be assigned a value of 1 ELISA unit/mL for GMT computations.

Secondary immunogenicity endpoints include the following:

- GMT Marburg GP protein-specific IgG ELISA antibody on all other study days through Day 181
- GMT PsVNT₅₀ and PsVNT₈₀ on all other study days to Day 181
- Seroconversion rate defined as at least 4-fold increase in Marburg GP-specific IgG (ELISA) titer compared to Day 1 for subjects with baseline titers > LLOQ. Otherwise, if baseline titer < LLOQ or <LOD, seroconversion is defined as at least 4-fold increase over LLOQ/2.
- Seroconversion rate defined as at least 4-fold increase in Marburg GP-specific neutralizing antibody titer PsVNA compared to Day 1 for subjects with baseline titers > LLOQ.

Otherwise, if baseline titer < LLOQ, seroconversion is defined as at least 4-fold increase over LLOQ/2.

- Geometric mean fold increase in Marburg GP-specific IgG (ELISA)
- Geometric mean fold increase in Marburg GP-specific neutralizing antibody titer (PsVNA)
- Seroresponse rate defined as at least 2-fold increase in Marburg GP-specific IgG (ELISA) compared to Day 1 for subjects with baseline titers > LLOQ. Otherwise, if baseline titer < LLOQ or <LOD, seroresponse is defined as at least 2-fold increase over LLOQ/2.
- Seroresponse rate defined as at least 2-fold increase in Marburg GP-specific neutralizing antibody titer PsVNA compared to Day 1 for subjects with baseline titers > LLOQ.
 Otherwise, if baseline titer < LLOQ, seroresponse is defined as at least 2-fold increase over LLOQ/2.
- Reverse cumulative distribution of titers (IgG ELISA and PsVNA)
- The correlation between the IgG ELISA and neutralizing antibody titers on all study days tested
- The correlation between blood viremia AUC and IgG ELISA and neutralizing antibody

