3.2. General Methods

All data listings that contain or imply an evaluation date will contain a relative study day (Rel Day). Pre-treatment and on-treatment study days are numbered relative to the day of the first dose of study medication which is designated as Day 1. The preceding day is Day -1, the day before that is Day -2, etc. Post-treatment study days are numbered relative to the first dose and are designated as Day 1, Day 2, etc. for table and listing display. Data for time interval analysis and graphing will be displayed as days since dosing where Hour 6 timepoint on Day 1 is converted to 0.25 days.

All outputs will be incorporated into Microsoft Word or Excel files, or Adobe Acrobat PDF files, sorted and labeled according to the International Conference on Harmonisation (ICH) recommendations, and formatted to the appropriate page size(s).

Tabulations will be produced for appropriate demographic, baseline, immunogenicity, and safety parameters. For categorical variables, summary tabulations of the number and percentage of subjects within each category (with a category for missing data) of the parameter will be presented. For continuous immunogenicity variables, the number of subjects, geometric mean, median, geometric standard deviation (SD), minimum, and maximum values will be presented.

Other continuous variables (e.g., BMI) will be summarized by the number of subjects, mean, median, SD, minimum, and maximum values. Summarizations will be tabulated by treatment group.

Formal statistical hypothesis testing will be performed on the primary and secondary immunogenicity endpoints with all tests conducted at the 2-sided, 0.05 level of significance. Summary statistics will be presented, as well as CIs on selected parameters, as described in the sections below.

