3.5. Methods of Pooling Data

In addition to presenting results by PHV01 vaccine dose levels, data will be pooled across PHV01 vaccine dose levels for analyses as an PHV01 overall group and all placebo subjects will be pooled as another group.

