4.3.3. Seroresponse Rate of ELISA Titers and PsVNT

Seroresponse is defined as a \geq 2-fold increase in the titer when compared to baseline (Day 1). If the baseline titer is <LLOQ or <LOD (ELISA only), a seroresponse is defined as titer greater than or equal to LLOQ.

The number, percent, and associated exact 95% CI of subjects whose baseline response is negative, i.e., less than the LLOQ, will be tabulated for each treatment group and the combined PHV01 vaccine group.

The number, percent, and exact 95% CI of seroresponse for Days 8 (if tested), 15, 29, 85 and 181 will be calculated. Comparisons between each PHV01 dose level with one another and with the placebo group will be performed using the Newcombe method.

Analyses of seroresponse rates will be performed separately for the ELISA IgG and neutralizing antibody titers.

4.3.4. Correlation between IgG ELISA and neutralizing antibody titers on Days 29, 85 and 181

Spearman's rank correlation will be used to estimate the association between IgG antibody titers and PsVNA titers for each PHV01 vaccine dose group including the combined PHV01 group at Days 29, 85, and 181.

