4.4.4. Vaccine Viremia Area Under the Curve

Vaccine viremia area under the curve (AUC) will be estimated using the trapezoid rule. Calculations will be performed relative to the first vaccination for each subject.

Calculations relative to the first vaccination will be based on figures displaying the number of copies of rVSV RNA on the Y axis and the actual number of days after the first vaccination that the blood sample was taken on the X axis. The general formula used to calculate AUC will be:

$$AUC_{i} = \sum_{i=0}^{n[\]} \frac{1}{2} \times [(RNA\ Copies_{k} - RNA\ Copies_{k-1})] \times [Days_{k} - Days_{k-1}]$$

Where the index i represents subject, index k represents the time points measured in actual days in which the viremia sample was drawn, 'RNA Copies' represents the base-10 log transformed number of rVSV RNA copies, and Days represents the actual days the blood sample for viremia was taken.

Two sets of AUC calculations will be performed: AUC from first vaccination to Day 8, and AUC from first vaccination to Day 29. These quantities summarize viremia after the first vaccination.

AUC from first vaccination to Day 8 will be calculated using the above formula where k = Days 1 (at 0 and 6 hours), 2, 4, and 8.

AUC from first vaccination to Day 29 will be calculated using the above formula where k = Days 1 (at 0 and 6 hours), 2, 4, 8, 15, 29.

Each set of AUC calculations will be summarized descriptively by the geometric mean AUC, geometric standard deviation, median, minimum, and maximum value, by treatment group. Descriptive statistics will also be presented for the combined PHV01 treatment group. Calculation of the geometric mean AUC and standard deviation will follow the approach outlined in Section 4.4.3.

Spearman's rank correlation will be used to estimate the association between viremia AUC and IgG ELISA antibody titers for each PHV01 vaccine dose group including the combined PHV01 group at Day 29. A similar analysis will be performed to estimate the correlation between viremia AUC and PsVNA titers.

Spearman's rank correlation will be used to estimate the association between the viremia AUC (Day 0 to 29) with the AE symptom index calculated for solicited local AEs that occurred from Day 0 to Day 29 for each vaccine dose group. The same analysis will be repeated using the AE symptom index calculated for systemic AEs.

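### The combined-group Spearman correlation of viremia AUC with Day 29 antibody ignores dose and so mixes within-dose with between-dose association; a dose-stratified correlation should be pre-specified beside it

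*SAP*

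**What the plan says.** SAP 4.4.4 plans Spearman correlations to "estimate the association between viremia AUC and IgG ELISA antibody titers for each PHV01 vaccine dose group including the combined PHV01 group", with titers taken from Day 29. It continues: "A similar analysis will be performed to estimate the correlation between viremia AUC and PsVNA titers". SAP 3.5 defines the combined group: "data will be pooled across PHV01 vaccine dose levels for analyses as an PHV01 overall group". Placebo is kept separate, so the combined group has 3 × 10 = 30 subjects.

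Neither section stratifies by dose or adjusts for it. SAP 3.6 leaves covariate adjustment to ad hoc exploratory work.

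On status, SAP 1.2.5.2 lists among the secondary immunogenicity endpoints "The correlation between blood viremia AUC and IgG ELISA and neutralizing antibody". SAP 3.2 says that testing will be "performed on the primary and secondary immunogenicity endpoints with all tests conducted at the 2-sided, 0.05 level of significance", and SAP 3.7 makes no multiplicity adjustment. Protocol 3.1.6 does not list this correlation; it is an addition made in the SAP.

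Elsewhere the SAP is more careful about pooling. In 4.4.3 the combined-group analysis of viremia duration is run only if the three dose groups' confidence intervals overlap. In the last paragraph of 4.4.4 the correlation of AUC with the symptom index is planned by dose group, with no combined group named.

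**The concern.** The natural question behind this endpoint is whether, among people given the same dose, those with more vaccine replication make more antibody. Dose was assigned over a 100-fold range (1×10⁵ to 1×10⁷ pfu). It is a recognised possible cause of both variables: Protocol 7.1 looks for a dose response in immunogenicity, and Protocol 7.5.1 models vaccinemia against dose.

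Ranking all 30 vaccinees together lets a shift in both variables between dose groups appear as a correlation between them. A reader could then take a dose effect for a biological link between viremia and antibody. The per-dose coefficients are free of this, but a group of 10 can show only a very strong correlation, so they give little protection against misreading the pooled value.

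**Working it through.** **Inputs.** There are 10 subjects per dose and 30 in the combined group, with a two-sided 0.05 level (SAP 3.1, 3.2). The within-group geometric SD of titer is 3.3 (SAP 3.1). Dose-effect sizes are not in the documents, so they are assumed and varied.

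**The plan's own figure.** The plan gives none for the correlation. Its sample-size figures do reproduce with a two-sample t-test and SD = ln 3.3: 6.41- and 8.59-fold for 10 v 6 at 80% and 90% power (stated 6.4 and 8.6), and 4.66- and 5.94-fold for 30 v 6 (stated 4.7 and 5.9). This supports 3.3 as the unit for translating shifts. A shift of *s* SD per dose step is a titer rise of 3.3^*s*: 1.35-fold at 0.25, 1.82-fold at 0.5, 2.45-fold at 0.75 and 3.3-fold at 1.

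**Why pooling creates a correlation.** Let AUC and log titer each have within-dose SD 1 and within-dose correlation ρ, and let them shift by *a* and *b* SD per dose step. Over three equal groups the step scores −1, 0, 1 have variance 2/3, so on the Pearson scale

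r(pooled) = (ρ + ⅔ab) / √[(1 + ⅔a²)(1 + ⅔b²)].

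With ρ = 0 and a = b this is ⅔a²/(1 + ⅔a²): 0.04, 0.14, 0.27 and 0.40 at a = 0.25, 0.5, 0.75 and 1. If either *a* or *b* is 0 it is 0. If a = b = 0 it equals ρ.

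**Thresholds for p<0.05.** |r| = t/√(n − 2 + t²). For n = 30 this is 2.048/√(28 + 4.194) = 0.36. For n = 10 it is 2.306/√(8 + 5.318) = 0.63.

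**Simulation with no within-dose association** (40,000 trials per row, normal variables without ties). The stratified test ranks within dose, combines the centred ranks and uses 30 − 3 − 1 = 26 df.

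| Shift per step, AUC / titer (SD) | Mean pooled r_s | Pooled test rejects | Stratified test rejects |
|---|---|---|---|
| 0 / 0 | 0.00 | 5% | 5% |
| 1 / 0 | 0.00 | 5% | 5% |
| 0.25 / 0.25 | 0.04 | about 6% | 5% |
| 0.5 / 0.5 | 0.14 | 12% | 5% |
| 0.75 / 0.75 | 0.28 | 32% | 5% |
| 1 / 1 | 0.41 | 66% | 5% |

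The sign can also reverse. With ρ = −0.3 and 1 SD shifts on both, the mean pooled r_s is about +0.25 and the stratified value about −0.26.

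**Power when the within-dose correlation is 0.5.**

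| Situation | Pooled | Stratified | One dose group (n = 10) |
|---|---|---|---|
| No dose effect | 77% | 67–68% | 27–29% |
| AUC +1 SD per step, titer affected only through AUC | 93% | 67–68% | 27–29% |

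A partial Spearman (overall ranks with dose-group means removed, 26 df) rejects 5.0–5.4% in the null rows above and has 73–74% power in the two power rows.

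**The case against.** - **The pooled coefficient is not meaningless.** One might infer that it tests only whether both variables rise with dose. That is too strong. It mixes both sources, and with no dose effect and ρ = 0.5 it has 77% power to find the within-dose association. This objection stands.
- **Dose may not move both variables.** The protocol speaks of a potential dose response (7.1) and of exploring the vaccinemia–dose relation (7.5.1). Protocol 1.3 says that a single low dose of a live vaccine is generally enough for primary immunization, which is compatible with a flat titer response. This stands: the inflation is conditional, and small for small shifts (AUC 1 SD with titer 0.25 SD gives 10%).
- **No documented decision uses it.** A reader might infer harm to Phase 2 dose selection. The documents do not support that. The interim analysis that guides dose choice (Protocol 7.2, SAP 3.12) does not list this correlation.
- **The 5% test is inferred.** SAP 4.4.4 speaks of estimation and names no null hypothesis, and SAP 3.1 says the sample was not sized for formal testing. Yet SAP 3.2 does cover secondary immunogenicity endpoints, and an estimate that mixes two associations can be misread without a p-value.
- **Between-dose association may be real signal.** If dose acts on antibody through replication, stratifying discards information (93% against 67–68% power). This is a good reason not to replace the pooled value.
- **Ties.** SAP 4.4.3 sets results below LOD to 1 copy/mL, which is 0 on the log10 scale, so AUCs can tie. If one dose group were wholly undetectable, naive combination would shrink a mean stratified value of 0.44 to about 0.44 × √(2/3) = 0.36. The fix needs a rule for this.
- **Extension to ELISA v PsVNA.** SAP 4.3.4 estimates the "association between IgG antibody titers and PsVNA titers for each PHV01 vaccine dose group including the combined PHV01 group". Correlating two antibody assays over the full response range is ordinary practice, so the concern does not carry over.

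**Conclusion.** The concern holds in a limited form. The combined-group correlations of AUC with ELISA and with PsVNA do not separate association at a given dose from differences between doses. The false-positive rate for within-dose association ranges from 5% (at most one variable depends on dose) to about 66% (both shift by 1 SD per step). The range rests on assumed linear shifts, normal variables and no ties, since the plan offers no dose-effect sizes. The planned per-dose correlations are unaffected but have under 30% power at ρ = 0.5.

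This concerns a secondary association measure added in the SAP. It touches no primary endpoint and no decision that the documents describe. It is a cheap improvement, not a defect that threatens the trial's conclusions.

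**What to change.** Amend SAP 4.4.4 for AUC v ELISA and AUC v PsVNA in the combined PHV01 group:

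- Pre-specify one dose-adjusted Spearman as the measure of association at a given dose: either within-dose ranks centred and combined, or a partial Spearman on dose as a three-level factor. Use 26 df and give a 95% CI by a stated method.
- State the rule for ties. For example, use mid-ranks, and leave a dose group whose AUCs are all tied out of the combination, with df reduced to 20 − 2 − 1 = 17.
- Keep the unadjusted pooled value beside it, labelled descriptive and as including the dose effect.
- Keep the per-dose correlations. Leave SAP 4.3.4 as it is.

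The cost is one SAP sentence and one extra analysis, with no new data. The stratified test has less power than the pooled one (67–68% against 77% with no dose effect, and against 93% if the dose effect on antibody runs wholly through viremia). The pooled value is kept as a labelled description for that reason.

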4.4.5. Laboratory Data

Clinical laboratory values will be expressed in standard international (SI) units and results will be graded by the local laboratory as low, normal, or high. Additionally, select parameters will also be graded in accordance with the FDA document "Guidance for Industry: Toxicity Grading Scale for Healthy Adult and Adolescent Volunteers Enrolled in Preventive Vaccine Clinical Trials" outlined in Table 5-4 and Table 5-5. For analyses purposes, results not meeting grading criteria will be graded as Grade 0.

Descriptive statistics for serum chemistry, hematology, and coagulation values at baseline, all scheduled post-baseline visits, and the last study visit will be summarized for each clinical laboratory parameter. In the event of repeat values, the last non-missing value per study day/time will be used. Change from baseline (Day 1) will be calculated for each subject as the value at the specified post-baseline study visit minus the baseline value. The descriptive statistics for actual and change from baseline will include: the mean, standard deviation, median, and range of all values for each test.

Shift tables of change in toxicity grade for select laboratory parameters from baseline to each scheduled post-baseline visit and from baseline to last value on study will also be presented by dose level, all PHV01 dose levels combined and placebo. The numbers and percentages of subjects in each treatment group who had values below, within, and above the normal range at baseline and at the last visit will also be presented.

The results of rVSV PCR from blood, urine, and saliva will be tabulated by visit and treatment group.

All laboratory data will be provided in data listings. A subset listing will be presented for all toxicity graded laboratory values and abnormal laboratory values.

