Blood Urea Nitrogen BUN (mg/dL)	23 – 26	27 – 31	> 31	Requires dialysis
Creatinine (mg/dL)	1.5 – 1.7	1.8 - 2.0	2.1 – 2.5	> 2.5 or requires dialysis
Glucose – Hypoglycemia mg/dL	65 – 69	55 – 64	45 – 54	< 45
Glucose – Hyperglycemia	100 – 110 110 – 125	111 – 125 126 – 200	>125 >200	Insulin requirements or hyperosmolar coma

TMP-BS-001 Statistical Analysis Plan Template

Version 3.0

Effective: 17 Aug 2020
Page 33 of 37

^b Oral temperature, no recent hot or cold beverages or smoking.

^c When resting heart rate is between 60 – 100 beats per minute. Use clinical judgement when characterizing bradycardia among some healthy subject populations, for example, conditioned athletes.

Serum ^{a,b}	Mild (Grade 1)	Moderate (Grade 2)	Severe (Grade 3)	Potentially Life Threatening (Grade 4)
Fasting – mg/dL Random – mg/dL				
Liver Function Tests - ALT, AST	1.1 – 2.5 × ULN	$2.6 - 5.0 \times ULN$	5.1 – 10 × ULN	> 10 × ULN
Bilirubin – accompanied by any increased LFT	1.1 – 1.25 × ULN	1.26 – 1.5 × ULN	1.51 – 1.75 × ULN	> 1.75 × ULN
Bilirubin – when LFT is normal	1.1 – 1.5 × ULN	$1.6 - 2.0 \times ULN$	$2.0 - 3.0 \times ULN$	> 3.0 × ULN

Abbreviations: ALT = alanine aminotransferase; AST = aspartate aminotransferase; BUN = blood urea nitrogen; PRBC = packed red blood cells; RBC = red blood cell; ULN = upper limit of normal

Table 5-5 Laboratory Toxicity Grading Scale for Hematology Adverse Events

Hematology Parameter ^a	Mild (Grade 1)	Moderate (Grade 2)	Severe (Grade 3)	Potentially Life Threatening (Grade 4)
PT – increase by factor (prothrombin time)	1.0 – 1.10 × ULN	1.11 – 1.20 × ULN	1.21 – 1.25 × ULN	> 1.25 × ULN
PTT – increase by factor (partial thromboplastin time)	1.0 – 1.2 × ULN	1.21 – 1.4 × ULN	1.41 – 1.5 × ULN	> 1.5 × ULN
Hemoglobin (Female) - gm/dL	11.0 - 12.0	9.5 - 10.9	8.0 - 9.4	< 8.0
Hemoglobin (Male) - gm/dL	12.5 - 13.5	10.5 - 12.4	8.5 - 10.4	< 8.5
WBC Increase - cell/mm ³	10,800 – 15,000	15,001 – 20,000	20,001 – 25, 000	> 25,000
WBC Decrease - cell/mm ³	2,500 – 3,500	1,500 – 2,499	1,000 – 1,499	< 1,000
Lymphocytes Decrease - cell/mm ³	750 - 1,000	500 - 749	250 - 499	< 250
Neutrophils Decrease - cell/mm ³	1,000 – 1,499	500-999	<500	Hospitalization
Eosinophils - cell/mm ³	650 - 1500	1501 - 5000	> 5000	Hospitalization
Platelets Decreased - cell/mm ³	125,000 – 140,000	100,000 – 124,000	25,000 – 99,000	< 25,000

Abbreviations: ULN = upper limit of normal; WBC = white blood cell.

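### Some laboratory toxicity bands in the SAP leave gaps, and its Grade 0 rule, read literally, grades in-between values below both neighbouring grades in the toxicity-grade tables

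*SAP*

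**What the plan says.** SAP 4.4.5 sets up two classifications of each laboratory result. The first is the laboratory's own: "Clinical laboratory values will be expressed in standard international (SI) units and results will be graded by the local laboratory as low, normal, or high". The second is a toxicity grade: "select parameters will also be graded in accordance with the FDA document", using Tables 5-4 and 5-5. The default for the second is: "For analyses purposes, results not meeting grading criteria will be graded as Grade 0".

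The grade feeds this output: "Shift tables of change in toxicity grade for select laboratory parameters from baseline to each scheduled post-baseline visit", and also the shift to the last value on study.

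Three outputs in the same section do not need the grade:

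- descriptive statistics of actual values and changes at every scheduled visit;
- a normal-range table of subjects "who had values below, within, and above the normal range at baseline and at the last visit will also be presented";
- a listing: "A subset listing will be presented for all toxicity graded laboratory values and abnormal laboratory values".

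The bands are printed as closed ranges. For platelets, Grade 1 is "125,000 – 140,000" and Grade 2 is "100,000 – 124,000" cells/mm3. ALT/AST, bilirubin, PT and PTT are graded as multiples of ULN; creatinine, BUN and glucose are in mg/dL. A footnote calls the table values guidelines. Neither document states a rounding, boundary or tie rule, or says whether grading comes before or after conversion to SI units. The bands in Protocol Appendix 1, Tables A4 and A5, are the same for these parameters.

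**The concern.** A grading scale should be monotone: a worse value never gets a lower grade. Where two bands do not meet, a value between them satisfies no criterion. The Grade 0 default then places it below both neighbours, so the error always understates severity.

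Normal and abnormal laboratory values are among the primary safety endpoints (Protocol 3.1.1, SAP 1.2.5.1). Protocol 7.5.1 also asks for post-vaccination abnormalities to be summarised by toxicity grade. With 10 subjects per dose and 6 on placebo, one misgraded subject moves a group percentage by 1/10 = 10 points or 1/6 = 16.7 points. Safety laboratory tests are drawn at screening and on Days 1, 4, 8 and 29. The normal-range table covers only baseline and the last visit, so a transient in-between value on Day 4 or Day 8 would be missing from it as well as misplaced in the grade shift table.

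**Working it through.** The plan gives no figure to reproduce. The check applies the printed bands with closed limits to each reportable value.

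**Formula.** For adjacent grades with limits given as multiples of ULN, a value v is in a gap if (end of lower band) x ULN < v < (start of next band) x ULN.

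**Inputs from SAP Tables 5-4 and 5-5 (x ULN).** ALT/AST 1.1-2.5, 2.6-5.0, 5.1-10. PT 1.0-1.10, 1.11-1.20, 1.21-1.25. PTT 1.0-1.2, 1.21-1.4, 1.41-1.5. Bilirubin with normal liver tests 1.1-1.5, 1.6-2.0, 2.0-3.0.

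**Assumptions, not in the documents.** Local ULNs, reporting resolution and SI conversion factors.

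| Test (assumed ULN, resolution) | Gap limits | Values in no band |
|---|---|---|
| ALT/AST (40 U/L, whole units) | 100 to 104; 200 to 204 | 101-103; 201-203 |
| PT (12.5 s, 0.1 s) | 13.75 to 13.875; 15.0 to 15.125 | 13.8; 15.1 |
| PTT (35 s, 0.1 s) | 42.0 to 42.35; 49.0 to 49.35 | 42.1-42.3; 49.1-49.3 |
| Bilirubin, normal liver tests (1.2 mg/dL, 0.1) | 1.80 to 1.92 | 1.9 |

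**Range over ULN.**

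- ALT/AST, ULN 30 to 60: 4 to 10 values (at 30: 76-77 and 151-152; at 60: 151-155 and 301-305).
- PT, ULN 12.0 to 14.5 s: 2 values each.
- PTT, ULN 32 to 40 s: 6 values each.
- Bilirubin with normal liver tests: 1 value at ULN 1.1, 1.2 and 1.3; none at 1.0.

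**Share of the graded scale lying in gaps.** ALT/AST 0.2/(10 - 1.1) = 2.2%; PT 0.02/0.25 = 8%; PTT 0.02/0.5 = 4%. These are widths, not expected frequencies of results.

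**Gaps that depend on precision or units.**

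- Platelets: none in whole thousands. In single cells, 99,001-99,999 and 124,001-124,999, which is 2 x 999 = 1,998 values.
- Creatinine: none at 0.1 mg/dL. At 0.01 mg/dL, 1.71-1.79 and 2.01-2.09, 18 values. On rounded SI values (factor 88.4), 1.7 to 1.8 mg/dL is 150.28 to 159.12 and 2.0 to 2.1 is 176.8 to 185.64, so 151-159 and 177-185 umol/L meet no band.
- BUN: none in whole mg/dL. In SI (2.801), 26 to 27 mg/dL is 9.28 to 9.64, so 9.3-9.6 mmol/L.
- Low glucose: none in whole mg/dL. In SI (18.016), 3.0 mmol/L = 54.05 and 3.6 mmol/L = 64.86 mg/dL meet no band.

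**No gap.** WBC, lymphocytes, neutrophils and eosinophils in whole cells; hemoglobin at 0.1 gm/dL; bilirubin with raised liver tests at 0.1 mg/dL for ULN 1.0 to 1.3.

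**Tie.** With normal liver tests, bilirubin Grade 2 ends and Grade 3 starts at 2.0 x ULN. At ULN 1.2 mg/dL, 2.4 mg/dL meets both.

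**How the grade depends on the closing rule (ALT, ULN 40).**

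| ALT | Ratio | As written | Lower band runs up to next | Round to 0.1 | Next band up |
|---|---|---|---|---|---|
| 101 | 2.525 | 0 | 1 | 1 | 2 |
| 203 | 5.075 | 0 | 2 | 3 | 3 |

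Any of the three closes the gaps. They do not agree with each other, so the choice has to be written down.

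**The case against.** The strongest reply is that the Grade 0 sentence most naturally covers values that do not reach Grade 1. A grade shift table needs such a category, and nothing states an intent to down-grade. Rounding to printed precision also removes every example: 101/40 = 2.525 gives 2.5 (Grade 1), 13.8/12.5 = 1.104 gives 1.10, 49.3/35 = 1.409 gives 1.41, and 1.9/1.2 = 1.58 gives 1.6. Both points are fair. But the documents state neither the limit to values below Grade 1 nor the rounding, and a programmer could code the sentence literally. This is a drafting gap with a wrong result if followed as written.

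Three stronger readings are tempting, and the documents do not support them:

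- **All laboratory bands have gaps.** Many do not at their printed precision, as listed in the working.
- **In-between values are analysed as normal.** That is true only of the toxicity-grade outputs. An ALT of 203 would still be flagged high by the laboratory, enter the descriptive statistics and appear in the abnormal-value listing.
- **Pausing or AESI decisions are affected.** A reader might infer this because the pausing rule refers to Grade 3 events and thrombocytopenia counts as an AESI from Grade 2. But the SAP rule is limited to analysis, and Protocol 6.5 has the Investigator assign severity, with Appendix 1 as guidance. Nothing shows that conduct decisions use the derived grade.

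**Conclusion.** The point holds in limited form. As printed, ALT/AST, PT, PTT and bilirubin with normal liver tests leave gaps at ordinary reporting resolution (bilirubin at three of the four ULNs tried). Applied literally, the Grade 0 default gives a non-monotone grade there. The bilirubin tie is a separate defect at a single boundary, which the Grade 0 rule does not cause.

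The size is small. The gaps are narrow, the trial has 36 healthy subjects, and few results are likely to be affected. The documents do not allow an expected count. The specific values rest on assumed ULNs and resolutions; the existence of gaps for ALT/AST, PT and PTT held at every ULN tried. The consequence is confined to toxicity-grade tabulations, where one subject is a visible fraction of a group.

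**What to change.** For analysis grading only, with no change to any clinical threshold:

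1. In SAP Section 5, either define contiguous bands or state, per parameter, the precision to which values are rounded before grading. PTT limits are printed with mixed decimals, so one general precision is not enough. Exact halves need a rule too (102/40 = 2.55).
2. State the units in which grading is done, and whether this precedes SI conversion.
3. Give bilirubin at 2.0 x ULN with normal liver tests a single analysis grade, reconciled with Protocol Appendix 1. If rounding to 0.1 is chosen, the tie widens to ratios from 1.95 to 2.05, so it must be settled under either option.
4. In SAP 4.4.5, limit Grade 0 to values that do not reach the Grade 1 limit.

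Contiguous bands or stated rounding leaves no in-between value at Grade 0 for any parameter checked. The cost is a footnote, one revised sentence and some grading code.
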